7.1. Discontinuation of Study Intervention

See the SoA (Sections 1.3.1, 1.3.2, and 1.3.3) for data to be collected at the time of early termination.

The DMC and FDA may recommend modifications to the protocol including discontinuation of study intervention upon review of safety data.

Study intervention may also be paused due to safety concerns at any time by the site investigator. The sponsor and DMC should be notified immediately if study intervention was paused.

7.1.1. Study Termination

The sponsor may stop the study (and/or the study center) for any reason with appropriate notification. The DMC and FDA may recommend study termination upon review of safety data.

7.2. Participant Discontinuation/Withdrawal from the Study

- A participant may withdraw from the study at any time at his/her own request, or may be withdrawn at any time at the discretion of the investigator for safety, behavioral, compliance, or administrative reasons. This is expected to be uncommon.
- The participant will be permanently discontinued both from the study intervention and from the study at that time.
- If the participant withdraws consent for disclosure of future information, the sponsor may retain and continue to use any data collected before such a withdrawal of consent.
- If a participant withdraws from the study, he/she may request destruction of any samples taken and not tested, and the investigator must document this in the site study records.
- At the time of discontinuing from the study, if possible, an EOS Visit should be conducted, as shown in the SoA (Sections [1.3.1](#), [1.3.2](#), and [1.3.3](#)).

7.3. Lost to Follow up

A participant will be considered lost to follow-up if he or she repeatedly fails to return for scheduled visits and is unable to be contacted by the study site.

The following actions must be taken if a participant fails to return to the clinic for a required study visit:

- The site must attempt to contact the participant and reschedule the missed visit as soon as possible and counsel the participant on the importance of maintaining the assigned visit schedule and ascertain whether or not the participant wishes to and/or should continue in the study.
- Before a participant is deemed lost to follow up, the investigator or designee must make every effort to regain contact with the participant (where possible, 3 telephone calls and, if necessary, a certified letter to the participant's last known mailing address or local equivalent methods). These contact attempts should be documented in the participant's medical record.
- Should the participant continue to be unreachable, he/she will be considered to have withdrawn from the study.

Discontinuation of specific sites or of the study as a whole are handled as part of Appendix 1, Section [10.1](#).

8. Study Assessments and Procedures

- Study procedures and their timing are summarized in the SoA (Sections 1.3.1, 1.3.2, and 1.3.3). Protocol waivers or exemptions are not allowed.
- Immediate safety concerns should be discussed with the sponsor immediately upon occurrence or awareness to determine if the participant should continue or discontinue study intervention.
- Adherence to the study design requirements, including those specified in the SoA, is essential and required for study conduct.
- All screening evaluations must be completed and reviewed to confirm that potential participants meet all eligibility criteria. The investigator will maintain a screening log to record details of all participants screened and to confirm eligibility or record reasons for screening failure, as applicable.
- Repeat or unscheduled samples may be taken for safety reasons or for technical issues with the samples.

8.1. Efficacy Assessments

Stage 1

No efficacy measures will be assessed in Stage 1. Pupil diameter (mesopic) will be assessed as a measure of target engagement.

Stages 2a and 2b

Efficacy assessments in Stages 2a and 2b are:

- Mesopic and photopic high contrast, binocular and monocular DCNVA (refer to Sections 1.3.2 and 1.3.3 for assessment timepoints)
- Mesopic and photopic high contrast, binocular and monocular DCIVA (only in Stage 2b; refer to Section 1.3.3 for assessment timepoints)

Measurement: Visual acuity for near (40-cm), intermediate (66-cm) and distance (4-meter) targets will be measured in mesopic and photopic conditions. Mesopic condition is defined as lighting 3.2 to 3.5 candelas per square meter (cd/m^2 ; 10 to 11 lux) measured at the target. Photopic condition is defined as lighting $\geq 80 cd/m^2$ (251 lux) measured at the target.

- Mesopic and photopic pupil diameter (distance and near) (refer to Sections 1.3.2 and 1.3.3 for assessment timepoints)
- Depth of focus (refer to Sections 1.3.2 and 1.3.3 for assessment timepoints)

Measurement: Depth of focus will be measured on each eye.

- Bulbar conjunctival hyperemia (refer to Sections 1.3.2 and 1.3.3 for assessment timepoints)

Measurements: Bulbar conjunctival hyperemia in each eye will be graded separately by the investigator using sponsor-provided reference photographs.

Assessment should be performed by the same evaluator whenever possible in the same facility. Illumination should be consistent throughout the study. **Note:** The bulbar conjunctival hyperemia assessment is a different assessment than the hyperemia scales described as part of the biomicroscopic examination (Appendix 8, Section 10.8).

- PRO Questionnaires (only in Stages 2a and 2b) (refer to Sections 1.3.2 and 1.3.3 for assessment timepoints)

Near Vision Presbyopia Task-based Questionnaire (NVPTQ): Comprised of 12 questions on 4 reading tasks (i.e., reading a paragraph from a book, reading excerpts from an article in a newspaper, reading a portion of a nutrition label, and reading a section from a restaurant menu).

Electronic Near Vision Presbyopia Task-based Questionnaire (e-NVPTQ) (iPhone/iPod version): Comprised of 5 questions on an electronic reading task (i.e., reading a text on iPhone or iPod)

Measurements (NVPTQ and e-NVPTQ):

- Participants will complete specific reading tasks under mesopic (for NVPTQ) and photopic (for e-NVPTQ) conditions without any near-vision correction.
- Participants will then answer 3 questions for each task (5 questions for e-NVPTQ), rating their vision-related reading ability and satisfaction with their vision-related reading ability.
- There is no explicit recall period used for the NVPTQ and e-NVPTQ; the intention is for participants to complete the questionnaire immediately after completing each task.

Presbyopia Impact and Coping Questionnaire (PICQ): Participants will answer 20 questions about the degree to which they were impacted by their difficulty seeing up close (e.g., found daily near vision tasks difficult, or experienced self-consciousness); or engaged in coping behaviors (e.g., changed the font size on electronic screens) during the previous 7 days.

Single-Item Patient Global Impression of Status (PGIS): Participants will answer a single question about their global impression of the status of their near-vision acuity in the past 7 days.

Single-Item Patient Global Impression of Change (PGIC): Participants will answer a single question about their global impression of change in their near-vision acuity.

Details are provided in the study procedure manual.

8.2. Safety Assessments

Planned timepoints for all safety assessments are provided in the SoA (Sections 1.3.1, 1.3.2, and 1.3.3).

8.2.1. Physical Examinations

- A complete physical examination will include, at a minimum, assessments of the cardiovascular, respiratory, gastrointestinal and neurological systems. Height (only at screening) and weight will also be measured and recorded.
- Investigators should pay special attention to clinical signs related to previous serious illnesses.
- Physical examinations should be completed by a professionally trained physician or health professional listed on Form FDA 1572 and licensed to perform physical examinations.

8.2.2. Vital Signs

Vital signs will be assessed as follows:

- Oral/axillary temperature, heart rate, respiration rate, and blood pressure will be assessed.
- Systolic and diastolic blood pressure and heart rate will be measured after participants have been at rest (seated) for at least 5 minutes in a quiet setting without distractions (e.g., television, cell phones). Blood pressure and pulse measurements will be assessed with a completely automated device. Manual techniques will be used only if an automated device is not available. Blood pressure will be recorded in mm Hg and heart rate will be recorded in bpm.

8.2.3. Electrocardiograms

- Sites shall transmit all study-required ECGs obtained to the ECG vendor, unless otherwise specified in the study procedure manual.
- A standard 12-lead ECG that measures PR, QRS, QT, QTc, QTcB, and QTcF intervals will be performed in the supine position at the nominal times (relative to the dosing times) as outlined in the SoA (Sections 1.3.1, 1.3.2, and 1.3.3).

8.2.4. Clinical Safety Laboratory Assessments

- See Appendix 2, Section 10.2 for the list of clinical laboratory tests to be performed and to the SoA (Sections 1.3.1, 1.3.2, and 1.3.3) for the timing and frequency.
- At screening, the investigator or sub-investigator will assess the clinical significance of any values outside the reference ranges provided by the laboratory, and participants with abnormalities judged to be clinically significant will be excluded from the study.
- The investigator must review the laboratory report, document this review, and record any clinically relevant changes occurring during the study in the AE section of the eCRF. The laboratory reports must be filed with the source documents. Clinically significant abnormal laboratory findings are those which are not associated with the underlying disease, unless judged by the investigator to be more severe than expected for the participant's condition.

CONFIDENTIAL
AGN-241622

- All laboratory tests with values considered clinically significantly abnormal during participation in the study or within 30 days after the last dose of study intervention should be repeated until the values return to normal or baseline or are no longer considered clinically significant by the investigator or medical safety physician.
 - If such values do not return to normal/baseline within a period of time judged reasonable by the investigator, the etiology should be identified and the sponsor notified.
 - All protocol-required laboratory assessments, as defined in Appendix 2, Section 10.2 must be conducted in accordance with the laboratory manual and the SoA.
 - If laboratory values from non-protocol specified laboratory assessments performed at the institution's local laboratory require a change in participant management or are considered clinically significant by the investigator (e.g., SAE or AE or dose modification), then the results must be recorded as an SAE or AE in the eCRF.
 - Urine dipstick kits may be used to conduct drugs-of-abuse screens and pregnancy tests and alcohol screen at the study center post-screening. Alternatively, a breathalyzer may be used for an alcohol screen.

8.2.5. Study Intervention Tolerability and Drop Comfort Assessments

The presence and severity of ocular symptoms will be elicited from the participant separately for their treated eye(s), as applicable. Symptoms including blurred vision, foreign body sensation, pain, burning/stinging, tearing, and itching will be classified using a 5-point grading scale with duration of symptoms immediately after the drop instillation of each dose of study intervention. If any other ocular symptoms are present, these will be captured.

Participants will be asked to rate the overall comfort of the eye drops using a 6-point scale (i.e., soothing, very comfortable, comfortable, uncomfortable, very uncomfortable, or intolerable) immediately after the drop instillation for the right and left eyes separately, as applicable. Refer to Sections 1.3.1, 1.3.2, and 1.3.3 for assessment timepoints. Details are outlined in Appendix 9, Section 10.9.

8.2.6. IOP

IOP should be measured only after the biomicroscopic exam is completed and must be measured prior to pupil dilation. Measurements will be taken using a Goldmann applanation tonometer affixed to a slit lamp with the participant seated. Both eyes will be tested, with the right eye preceding the left eye. Refer to Sections 1.3.1, 1.3.2, and 1.3.3 for assessment timepoints. Details are outlined in Appendix 11, Section 10.11.

8.2.7. Slit lamp Biomicroscopy

Biomicroscopic examinations will be performed using a slit lamp. The examinations will include evaluation of the condition of the eyelids, conjunctiva, cornea, anterior chamber, iris/pupil, and sodium fluorescein corneal staining. Refer to Sections 1.3.1, 1.3.2, and 1.3.3 for assessment timepoints. Details are outlined in Appendix 8, Section 10.8.

8.2.8. Sodium Fluorescein Corneal Staining

Sodium fluorescein corneal staining assessments will be assessed and graded according to the Oxford Scale per Appendix 8, Section 10.8. Refer to Sections 1.3.1, 1.3.2, and 1.3.3 for assessment timepoints. Details are outlined in Appendix 8, Section 10.8.

8.2.9. Dilated Fundoscopic Examination

The fundus (indirect) ophthalmoscope examination assessments should be conducted through a dilated pupil. The examinations will include evaluation of the lens, vitreous, fundus, and optic nerve. The cup to disc ratio will be assessed. The investigator should note if the pupil dilated normally. Refer to Sections 1.3.1, 1.3.2, and 1.3.3 for assessment timepoints. Details are outlined in Appendix 10, Section 10.10.

8.2.10. Contrast Sensitivity (Stages 2a and 2b only)

Contrast sensitivity assessments will be conducted with participant's best distance correction, except for participants in Cohort 8, for which contrast sensitivity will be conducted with habitual distance correction. Refer to Sections 1.3.2 and 1.3.3 for assessment timepoints. Details will be outlined in the study procedures manual.

8.2.11. Photopic and Mesopic High-contrast CDVA (Stages 2a and 2b only)

Photopic and mesopic high-contrast CDVA will be conducted with the participant's best distance correction, except for participants in Cohort 8, for which photopic and mesopic high-contrast CDVA will be conducted with the participant's habitual distance correction. The assessment is to be measured binocularly. Pupil diameter must be measured in each individual eye. Refer to Sections 1.3.2 and 1.3.3 for assessment timepoints.

For all lighting conditions, different charts must be used for the repeated visual acuity measures within the same day.

Details will be outlined in the study procedures manual.

8.2.12. Manifest Refraction (Stages 2a and 2b only)

Manifest refraction (distance and near, mesopic and photopic) will be performed according to standard clinical practice in both mesopic and photopic conditions. If a participant loses ≥ 1 line of CDVA or DCNVA compared with Hour 0 of the same study visit at Hour 1 after dosing, a manifest refraction should be repeated under the same lighting conditions.

Refer to Sections 1.3.2 and 1.3.3 for assessment timepoints. Details will be outlined in the study procedures manual.

8.3. Adverse Events and Serious Adverse Events

The definitions of an AE or SAE can be found in Appendix 3, Section 10.3.

AEs will be reported by the participant.

CONFIDENTIAL
AGN-241622

The investigator and any qualified designees are responsible for detecting, documenting, and recording events that meet the definition of an AE or SAE and any other study-specific terms as relevant and remain responsible for following up AEs that are serious, considered related to the study intervention or study procedures, or that caused the participant to discontinue the study intervention/study (see Section 7).

8.3.1. Time Period and Frequency for Collecting AE and SAE Information

All AEs from the signing of the ICF until EOS Visit will be collected at the timepoints specified in the SoA (Sections 1.3.1, 1.3.2, and 1.3.3), and as observed or reported spontaneously by study participants.

All SAEs from the signing of the ICF until up to 30 days after last dosing will be collected at the timepoints specified in the SoA (Sections 1.3.1, 1.3.2, and 1.3.3), and as observed or reported spontaneously by study participants.

Medical occurrences that begin before the start of study intervention but after obtaining informed consent will be recorded in the AE section of the eCRF and will be considered pretreatment AEs.

All SAEs will be recorded and reported to the sponsor or designee immediately and under no circumstance should this exceed 24 hours, as indicated in Appendix 3, Section 10.3. The investigator will submit any updated SAE data to the sponsor within 24 hours of it being available.

Investigators are not obligated to actively seek AE or SAE information after conclusion of the study participation. However, if the investigator learns of any SAE, including a death, at any time after a participant has been discharged from the study, and he/she considers the event to be reasonably related to the study intervention or study participation, the investigator must promptly notify the sponsor.

8.3.2. Method of Detecting AEs and SAEs

The method of recording, evaluating, and assessing causality of AEs and SAEs and the procedures for completing and transmitting SAE reports are provided in Appendix 3, Section 10.3.

Care will be taken not to introduce bias when detecting AEs and/or SAEs. Open-ended and non-leading verbal questioning of the participant is the preferred method to inquire about AE occurrences.

8.3.3. Follow-up of AEs and SAEs

After the initial AE/SAE report, the investigator is required to proactively follow each participant at subsequent visits/contacts. All SAEs will be followed until resolution, stabilization, the event is otherwise explained, or the participant is lost to follow-up (as defined in Section 7.3). Further information on follow-up procedures is provided in Appendix 3, Section 10.3.

8.3.4. Regulatory Reporting Requirements for SAEs

- Prompt notification by the investigator to the sponsor of a SAE is essential so that Legal obligations and ethical responsibilities towards the safety of participants and the safety of a study intervention under clinical investigation are met.
- The sponsor has a Legal responsibility to notify both the local regulatory authority and other regulatory agencies about the safety of a study intervention under clinical investigation. The sponsor will comply with country-specific regulatory requirements relating to safety reporting to the regulatory authority, IRB/IEC, and investigators.
- An investigator who receives an investigator safety report describing an SAE or other specific safety information (e.g., summary or listing of SAEs) from the sponsor will review and then file it along with the investigator's brochure and will notify the IRB/IEC, if appropriate, according to local requirements.
- Investigator safety reports must be prepared for SUSARs according to local regulatory requirements and sponsor policy and forwarded to investigators as necessary.

8.3.5. Pregnancy

- Details of all pregnancies in female participants, and if indicated, female partners of male participants, will be collected from signing of the ICF and until the EOS.
- If a pregnancy is reported, the investigator should inform the sponsor or designee within 24 hours of learning of the pregnancy and should follow the procedures outlined in Appendix 7, Section 10.7.
- Abnormal pregnancy outcomes (e.g., spontaneous abortion, fetal death, stillbirth, congenital anomalies, ectopic pregnancy) or genetic abnormalities (whether leading to an elective abortion or not) are considered SAEs.

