Intervention Groups and Duration: The study duration is approximately 20 days for Stage 1 (including 18 days for screening, 1 day for study intervention, and the EOS Visit on Day 2); and approximately 60 days each for Stages 2a and 2b (including 30 days for screening, 14 days for study intervention, and the EOS Visit on Day 30).

[figure not shown]
Study Interventions by Study Stage and Cohort			
Stage 1	Single Ascending Dose in Healthy Participants		
	
Cohort 1 AGN-241622 [REDACTED] single dose left eye 9 Active; 3 Vehicle
	
Cohort 2 AGN-241622 [REDACTED] single dose left eye 9 Active; 3 Vehicle
	
Cohort 3 AGN-241622 [REDACTED] single dose left eye 9 Active; 3 Vehicle

Stage 2a	Multiple Ascending Dose in Participants with Presbyopia		
	
Cohort 4 AGN-241622 [REDACTED] QD × 14 days both eyes 9 Active; 3 Vehicle
	
Cohort 5 AGN-241622 [REDACTED] QD × 14 days both eyes 9 Active; 3 Vehicle
	
Cohort 6 AGN-241622 [REDACTED] QD × 14 days both eyes 9 Active; 3 Vehicle

Stage 2b	Multiple-Dose Exploratory Cohorts in Participants with Presbyopia		
	
Cohort 7 AGN-241622 (dose strength TBD) versus pilocarpine HCl [REDACTED] 1.25% QD × 14 days both eyes 60 (30 per treatment arm)
	
Cohort 8 AGN-241622 (dose strength TBD) (in participants who wear contact lenses) QD × 14 days both eyes 9 Active; 3 Vehicle
	

Data Monitoring Committee: Yes

CONFIDENTIAL
AGN-241622

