5.1.2. Stages 2a and 2b

1.	Age
1.01	Participant must be 40 to 65 years of age inclusive, at the time of signing the informed consent
2.	Type of Participant and Presbyopia Characteristics
2.01	In good general health at the Screening Visit, as determined by the investigator
2.02	[REDACTED]
2.03	Be nonsmoking and a nonuser of nicotine-containing products (never smoked or used nicotine-containing products or have not smoked or used nicotine-containing products within the previous 1 year)
2.04	[REDACTED]

3.	Sex
3.01	Male or female
4.	Informed Consent
4.01	Capable of giving signed informed consent, which includes compliance with the requirements and restrictions listed in the ICF and in this protocol
4.02	Written informed consent from the participant has been obtained prior to any study-related procedures
4.03	Written documentation has been obtained in accordance with the relevant country and local privacy requirements, where applicable
5.	

CONFIDENTIAL
AGN-241622

5.02	Female participants must be willing to minimize the risk of inducing pregnancy throughout the study, up through 30 days after the last dose of study intervention (refer to Appendix 7, Section 10.7)
	
A female participant is eligible if at least 1 of the following conditions applies:
 
 a. She is not a female of childbearing potential as defined in Appendix 7, Section 10.7 
OR
 
 b. She is a female of childbearing potential who agrees to follow the contraceptive guidance in Appendix 7, Section 10.7 throughout the study 
In addition, all female participants of childbearing potential must test negative for pregnancy at Screening (serum test) and on Day 1 (urine test).

6.	Other
6.01	Able, as assessed by the investigator, and willing to follow study instructions and likely to complete all required study visits

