10.7. Appendix 7: Contraceptive Guidance and Collection of Pregnancy Information

Definitions:

Woman of Childbearing Potential

A woman is considered fertile following menarche and until becoming post-menopausal unless permanently sterile (see below).

If fertility is unclear (e.g., amenorrhea in adolescents or athletes) and a menstrual cycle cannot be confirmed before first dose of study intervention, additional evaluation should be considered.

Women in the following categories are not considered WOCBP

1. Premenarchal
2. Premenopausal female with one of the following:
 - Documented hysterectomy
 - Documented bilateral salpingectomy
 - Documented bilateral oophorectomy

For individuals with permanent infertility due to an alternate medical cause other than the above, (e.g., mullerian agenesis, androgen insensitivity), investigator discretion should be applied to determining study entry.

Note: Documentation can come from the site personnel's: review of the participant's medical records, medical examination, or medical history interview.

3. Postmenopausal female
 - A postmenopausal state is defined as no menses for 12 months without an alternative medical cause.

Contraception Guidance:

Male Participants

Nonvasectomized male participants with female partners of childbearing potential are eligible to participate if they agree to ONE of the following during the protocol-defined timeframe in Section 5.1:

- Are abstinent from penile-vaginal intercourse as their usual and preferred lifestyle (abstinent on a long-term and persistent basis) and agree to remain abstinent
- Agree to use a male condom with spermicide plus partner use of a contraceptive method with a failure rate of < 1% per year as described in [Table 10-2](#) when having penile-vaginal intercourse with a woman of childbearing potential who is not currently pregnant

In addition, nonvasectomized male participants must refrain from donating sperm throughout the study, up through 30 days after the last dose of study intervention.

CONFIDENTIAL
AGN-241622

Nonvasectomized male participants with a pregnant or breastfeeding partner must agree to remain abstinent from penile-vaginal intercourse or use a male condom during each episode of penile penetration during the protocol-defined timeframe.

Female Participants

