Collection of Pregnancy Information

Male participants with partners who become pregnant

- The investigator will attempt to collect pregnancy information on any male participant's female partner who becomes pregnant while the male participant is in this study. This applies only to male participants who receive study intervention.
- After obtaining the necessary signed informed consent from the pregnant female partner directly, the investigator will record pregnancy information on the appropriate form and submit it to the sponsor within 24 hours of learning of the partner's pregnancy. The female partner will also be followed to determine the outcome of the pregnancy. Information on the status of the mother and child will be forwarded to the sponsor. Generally, the follow-up will be no longer than 6 to 8 weeks following the estimated delivery date. Any termination of the pregnancy will be reported regardless of fetal status (presence or absence of anomalies) or indication for the procedure.

Female Participants who become pregnant

- The investigator will collect pregnancy information on any female participant who becomes pregnant while participating in this study. The initial information will be recorded on the appropriate form and submitted to the sponsor within 24 hours of learning of a participant's pregnancy.
- The participant will be followed to determine the outcome of the pregnancy. The investigator will collect follow-up information on the participant and the neonate and the information will be forwarded to the sponsor. Generally, follow-up will not be required for longer than 6 to 8 weeks beyond the estimated delivery date. Any termination of pregnancy will be reported, regardless of fetal status (presence or absence of anomalies) or indication for the procedure.
- While pregnancy itself is not considered to be an AE or SAE, any pregnancy complication will be reported as an AE or SAE.
- Abnormal pregnancy outcomes (e.g., spontaneous abortion, fetal death, stillbirth, congenital anomalies, ectopic pregnancy) or genetic abnormalities (whether leading to an elective abortion or not) are always considered to be SAEs and will be reported as such.

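### Pregnancy collection ends at the EOS while SAE collection runs to 30 days after last dose, so an uncomplicated exposed pregnancy recognised after EOS is not clearly collected

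*Protocol*

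**What the plan says.** Section 8.3.5 states that pregnancies in female participants and, where indicated, in partners of male participants "will be collected from signing of the ICF and until the EOS". Appendix 7 (10.7) uses a participant-level trigger: the woman, or the male participant's partner, becomes pregnant while the participant is in the study. Once a pregnancy is collected, follow-up generally runs to 6 to 8 weeks past the estimated delivery date.

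Other rules in the protocol use a longer window:

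- **SAEs (8.3.1):** "All SAEs from the signing of the ICF until up to 30 days after last dosing will be collected".
- **TEAEs (9.4.2.1):** events more than 30 days after the last dose are not counted.
- **Sperm donation (Appendix 7, no stage limit):** nonvasectomized men "must refrain from donating sperm throughout the study, up through 30 days after the last dose of study intervention".
- **Female contraception (5.1.2, Stages 2a and 2b):** "Female participants must be willing to minimize the risk of inducing pregnancy throughout the study, up through 30 days after the last dose".

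The Synopsis gives the timing of EOS. Stage 1 has "1 day for study intervention, and the EOS Visit on Day 2" and Stage 2 has "14 days for study intervention, and the EOS Visit on Day 30".

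Appendix 7 says that abnormal pregnancy outcomes "are always considered to be SAEs and will be reported as such", and that pregnancy itself is neither an AE nor an SAE. After the study, a pregnancy-related SAE is reported only if the investigator judges it reasonably related, and the investigator need not seek it out.

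**The concern.** The protocol uses 30 days after last dose as its post-treatment horizon in several places, but stops collecting pregnancies earlier. Stage 1 shows the mismatch most plainly. Women of childbearing potential have a urine test on Day -1, the single dose is on Day 1 and the EOS Visit is on Day 2. A pregnancy conceived around or after dosing would not be recognised by then.

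What is at stake is the start of follow-up. Outcomes such as congenital anomaly normally become known long after a 30-day SAE window has closed. The provision that reaches them is Appendix 7's follow-up to delivery, and that begins only if the pregnancy is collected. For a new chemical entity given to humans for the first time, a complete record of exposed pregnancies is also the denominator against which any poor outcome would be judged.

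**Working it through.** The plan gives no figure to reproduce, so the check is day arithmetic followed by a comparison of the rules.

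**Inputs.** Last dose is Day 1 in Stage 1 and Day 14 in Stage 2. The EOS Visit is Day 2 in Stage 1 and Day 30 in Stage 2 (Synopsis). The comparison window is 30 days after last dose (8.3.1, 9.4.2.1, Appendix 7, 5.1.2).

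**Reading A: EOS is the participant's EOS Visit.** Let D be the day of last dose and E the day of the EOS Visit. Covered days = E − D; window end = D + 30; uncovered days = D + 30 − E.

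| Stage | D | E | Window end | Covered | Uncovered | Share uncovered |
|---|---|---|---|---|---|---|
| 1 | 1 | 2 | Day 31 | 2 − 1 = 1 | 31 − 2 = 29 | 29/30 = 97% |
| 2 | 14 | 30 | Day 44 | 30 − 14 = 16 | 44 − 30 = 14 | 14/30 = 47% |

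These figures assume scheduled visits. Under 7.2, a participant who withdraws leaves treatment and study together and has the EOS Visit at that point if possible, so the uncovered part can then be longer.

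**Reading B: EOS is the study-level end in 4.4, the last participant's last visit.** Let L be the date of that visit and d a participant's last-dose date. Uncovered days = max(0, d + 30 − L). For Stage 1 participants the gap shrinks, and it is zero once L is at least 30 days after their dose. For a last participant in Stage 2, L = d + 16, so the gap is 30 − 16 = 14 days.

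**What falls in the gap.** Four cases need separating:

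1. An abnormal outcome within 30 days of last dose is an SAE and is collectable under 8.3.1.
2. An abnormal outcome after 30 days is reportable only if the investigator learns of it and judges it related (8.3.1, Appendix 7).
3. An uncomplicated pregnancy conceived before EOS and recognised afterwards arguably meets the Appendix 7 trigger, but lies outside the 8.3.5 window if that window turns on when the pregnancy comes to light.
4. An uncomplicated pregnancy conceived after the participant's EOS Visit but within 30 days of last dose falls outside Appendix 7, and outside 8.3.5 on reading A.

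Cases 3 and 4 are the gap.

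**The case against.** The strongest reply is that the harmful events are largely covered already. Abnormal outcomes are SAEs, SAEs are collected to 30 days, and related SAEs learned of later must still be reported. A reader might infer that abnormal outcomes between EOS and day 30 would be lost. The documents do not support that, and this part of the objection stands.

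A reader might also infer that a Stage 1 pregnancy cannot be captured at all. That goes too far. Appendix 7 turns on when the woman becomes pregnant, not on when it is noticed, and the 24-hour notification rule in 8.3.5 has no cut-off of its own. A report after Day 2 could reasonably be accepted. What remains is that 8.3.5 and Appendix 7 do not say so consistently.

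A third point is the meaning of EOS. Section 8.3.1 ends AE collection at the EOS Visit, while 8.3.5 says only the EOS, which 4.4 could define at study level. The 29-day figure therefore depends on reading A. Appendix 7's participant-level wording favours that reading, and the 14 days for the last Stage 2 participants survive either one.

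Finally, it is tempting to say that the protocol sets a 30-day pregnancy-risk period for Stage 1 women. The visible 30-day contraception text is for Stages 2a and 2b. The corresponding Stage 1 item is not shown in the public text, and nothing should be inferred from its absence. For Stage 1 the comparison rests on the SAE window, the TEAE cutoff and the sperm-donation rule. The schedule tables are not shown either, so a pregnancy test at EOS cannot be checked; a test on Day 2 would not in any case detect a conception around dosing.

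**Conclusion.** The mismatch is real and small. On the participant-level reading, pregnancy collection leaves 29 of 30 days uncovered in Stage 1 and 14 of 30 in Stage 2. On the study-level reading, the Stage 1 gap shrinks or closes and up to 14 days remain for the last Stage 2 participants. The consequence is confined to exposed pregnancies that are so far uncomplicated and are recognised after EOS: these are not clearly collected or followed to outcome. The conclusion assumes scheduled visits and takes the 30-day SAE window as the natural comparator. Ages 40 to 65 and the contraception requirements mean that few such pregnancies are expected. The SAP (1.0) reports that the study ended after Stage 2a, so the point bears mainly on reporting and on any further study of the compound.

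**What to change.** In 8.3.5, run pregnancy collection from consent to the later of the participant's EOS Visit and 30 days after that participant's last dose. Naming the EOS Visit removes the ambiguity with 4.4. Align the Appendix 7 triggers for female participants and for partners to the same period, and state that a pregnancy conceived within it is collected even if recognised later. Ask about pregnancy in whatever contact is used to collect SAEs to 30 days.

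As dosing has ended, the equivalent steps now are to check whether any pregnancy was reported after EOS, to state the collection window in the study report, and to carry the corrected wording into later protocols.

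The cost is an edit to two sections, slightly longer passive follow-up and a few more records; the wording itself needs no new visit or test. Its limit should be stated: without an active contact at 30 days, Stage 1 would still depend on spontaneous reports. If no such contact exists for SAEs, adding one would be a separate cost.
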